Cancer patients undergoing surgery treatment	
It has been well established that major surgery itself increases the risk of VTE even in the absence of cancer. [9]. Historical data from 1970s and 1980s using routine screening procedures reported a 37% incidence of deep vein thrombosis (DVT) following general surgery in patients with cancer, in contrast to an estimated risk of 20% in patients without cancer. [10]. However, changes in surgical techniques, use of perioperative chemotherapy, and the practice of early postoperative mobilization with increased awareness of perioperative VTE likely have altered VTE incidence over time.
 
The absolute VTE risk varies with the type of surgery, including site, technique (e.g., open vs. laparoscopic approach), duration of surgery, type of anesthesia, the presence of postoperative infection and immobilization, and patients' comorbidities (e.g., body mass index [BMI] and previous history of VTE). Surgeries for resection of malignant tumors are associated with a particularly high risk of VTE likely because of the extensive vascular injury from tumor invasion and dissection as well as lengthy operation time, and in some cases, residual tumor or nodal mass continues to cause venous compression and stasis. Prolonged postoperative immobility is also quite common in these patients.
 
The risk of thrombosis is not only increased during the immediate postoperative period but also extends at least up to 30 days or even longer after surgery. In the @RISTOS study that prospectively followed 2,373 patients who underwent surgery for cancer, 40% of symptomatic VTE occurred more than 3 weeks after surgery and 46% of deaths were due to fatal pulmonary embolism (PE). [11] The investigators of the @RISTOS study found that a previous history of VTE, anesthesia lasting 2 hours or longer, bed rest for 4 days or longer, advanced tumor stage, and age 60 years or older were significant risk factors for VTE. Similarly, in the Million Women Study, the incidence of symptomatic VTE was observed to peak at 3 weeks postoperatively for all surgeries, but the risk remained

high up to 4 to 12 months for cancer patients.[12]. Relative to patients without cancer, the risk of VTE after surgery for cancer was 91-fold higher at 6 weeks, 53-fold at 7 to 12 weeks, and 34-fold at 4 to 12 months after surgery.

Estimated risk of venous thromboembolism associated with various types of surgery 13

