Surgical setting	Incidence of DVT, %	Incidence of PE, %
Major abdominal and pelvic surgery (colorectal/gynecological)	15–40 ^a	1.3–2 ^d
Major open urological surgery	15–40 ^a	0.2 ^e
Neurosurgery	15–40 ^a	Insufficient data
Thoracic surgery	4–14 ^a	5–12 ^f
Breast surgery	0.8–2.1 ^b	Insufficient data
Laparoscopic surgery	1–11 ^c	Insufficient data

Abbreviations: DVT, deep vein thrombosis; PE, pulmonary embolism.

Source: Adapted and modified from Geerts et al.¹⁶

^aRoutine screening of asymptomatic patients without prophylaxis.

^bSymptomatic patients without prophylaxis or mechanical prophylaxis alone (from retrospective studies).

^cRoutine screening of asymptomatic patients with or without prophylaxis.

^dSymptomatic patients without prophylaxis.

^eSymptomatic patients without prophylaxis or mechanical prophylaxis alone.

^fRoutine screening of asymptomatic patients with CT chest.

Pharmacological Prophylaxis

Pharmacological Prophylaxis for cancer patients undergoing surgery

Studies in the late 1980s and early 1990s showed that pharmacological prophylaxis reduces the risk of postoperative VTE by 60% compared with no prophylaxis.[14-17]

LMWH is generally the preferred choice of anticoagulant over UFH based on its ease of administration (once daily vs. twice to three times per day for UFH) and lower risk of heparin-induced thrombocytopenia (HIT).

Cancer patients may also tolerate higher doses of LMWH without increasing the bleeding risk further.[18]

The optimal duration of thromboprophylaxis after cancer surgery has not been established and the available data are limited to major abdominal and pelvic surgery. Although studies have shown that a longer duration of prophylaxis up to 1 month after major abdominal and pelvic surgery can further reduce the risk of VTE compared with standard duration (typically while in hospital or up to 7–10 days) [19-21]

In the ENOXACAN II trial, patients who received extended thromboprophylaxis (ETP) with LMWH up to 30 days after open surgery for abdominal and pelvic cancer had a 60% VTE risk reduction (95% CI: 10–82%), compared with those who received standard duration of 6 to 10 days (4.8 vs. 12%; $p = 0.02$).[19]

These findings are supported by a recent meta-analysis of seven RCTs and prospective studies which concluded that ETP is associated with a significant risk reduction of all VTE (2.6 vs. 5.6%; (RR: 0.44, 95% CI:

[figure not shown]
0.28–0.70) and proximal DVT (1.4 vs. 2.8%; RR: 0.46, 95% CI: 0.23–0.91). [22]

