3. ECOG >2
4. Life expectancy <6 months
5. Not signed informed consent

Study Duration	Each subject's participation will last from inclusion (enrolment visit) to follow up visit (if applicable; four weeks post hospital discharge) The entire study is expected to last by the end of 2019
Study Phases	(1) Screening : screening for eligibility, obtaining consent and administer thromboprophylaxis
Screening	
Study Treatment	(2) Observation Period : monitoring subjects over treatment time
Treatment	(3) Follow-up Phase (only if applicable e.g. by the end of treatment period)
Follow-Up	
Efficacy Evaluations	
 • Symptomatic/Suspected vein thromboembolism, including pulmonary embolism and deep vein thrombosis 
Confirmation of symptomatic PE requires symptoms of PE and one of the following findings
 
 1. A (new) intraluminal filling defect in (sub) segmental or more proximal branches on spiral CT scan; 2. A (new) intraluminal filling defect or an extension of an existing defect or a new sudden cut-off of vessels on the pulmonary angiogram;

3. A (new) considerable perfusion defect (~ 75% of a segment) with a local normal ventilation result (high-probability) on ventilation/perfusion lung scintigraphy (V/Q scan);
4. An inconclusive lung scan accompanied by documentation of (new) DVT in the lower extremities e.g., by compression ultrasound or venography.
 - Confirmation of symptomatic DVT requires symptoms of DVT and:
 - 1. A (new) noncompressible venous segment on ultrasonography
 - Incidental PE with one of the following:
 1. A (new) intra-luminal filling defect on CT scan, MRI scan, or pulmonary angiogram;
 - An inconclusive lung scan accompanied by documentation of (new) DVT in the lower extremities e.g., by compression ultrasound or venography.
 - Fatal PE is:
 1. PE based on objective diagnostic testing or autopsy or
 2. death not attributed to a documented cause and for which DVT/PE cannot be ruled out
 - Incidental DVT with the following finding:

Confirmation of recurrent incidental DVT requires inconclusive or no-symptoms of DVT and:

1. A (new) noncompressible venous segment on ultrasonography

Safety Evaluations Major, clinically relevant non-major bleeding, and minor bleeding

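### The incidental DVT rule is headed for any incidental DVT, but its only confirmation sentence is limited to recurrent ones

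*Combined protocol and SAP*

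**What the plan says.** The Efficacy Evaluations section opens with the line "Symptomatic/Suspected vein thromboembolism, including pulmonary embolism and deep vein thrombosis" and then sets out five event categories: symptomatic PE, symptomatic DVT, incidental PE, fatal PE and incidental DVT.

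The last category is headed "Incidental DVT with the following finding". One sentence follows, "Confirmation of recurrent incidental DVT requires inconclusive or no-symptoms of DVT and", and then a single numbered finding: "A (new) noncompressible venous segment on ultrasonography". The symptomatic DVT rule, introduced by "Confirmation of symptomatic DVT requires symptoms of DVT and", lists the same single finding and does not restrict itself to recurrent events.

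The symptomatic and incidental PE rules each include this alternative: "An inconclusive lung scan accompanied by documentation of (new) DVT in the lower extremities e.g., by compression ultrasound or venography".

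The Study Objective names the number of thrombotic events as the first of four foci. The Study Design section gives VTE events as the efficacy data to be collected.

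**The concern.** The heading and the sentence define different sets of events. The heading takes in every incidental DVT. The sentence, read as written, takes in only those in patients who have had one before. Nothing else in the section provides for a first incidental DVT.

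At stake is the event count. The Statistical And Analytic Plan is mainly descriptive, so the number of thrombotic events will be reported largely as recorded. The documents describe no central adjudication of events. Authorized staff review case report forms for completeness without direct access to patient records, although they may ask the hospital for more information. A difference in how sites read the rule could therefore pass into the reported figures.

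**Working it through.** The documents give no sample size, event target or expected VTE rate for this cohort, so there is no plan figure to reproduce. The check is a comparison of the rules.

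**Step 1. Compare the five categories in Efficacy Evaluations.**

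| Category | Limited to recurrent events? | Venography named as evidence of DVT? |
|---|---|---|
| Symptomatic PE | No | Yes, beside an inconclusive lung scan |
| Symptomatic DVT | No | No |
| Incidental PE | No | Yes, beside an inconclusive lung scan |
| Fatal PE | No | No |
| Incidental DVT | Heading: no. Sentence: yes | No |

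The restriction appears in 1 of 5 categories, and there only in the sentence. Venography is named in 2 of 3 PE rules and 0 of 2 DVT rules.

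**Step 2. Look for a reason for the restriction.** The inclusion criteria cover cancer type with surgery, age, performance status, life expectancy and consent, and the exclusion criteria mirror them. None requires a previous VTE. The background treats previous VTE as something that varies between patients. It is the first of five risk factors reported from a cited surgical cohort: "a previous history of VTE, anesthesia lasting 2 hours or longer, bed rest for 4 days or longer", followed by advanced tumor stage and older age. First events are therefore to be expected in this population, and the documents give no reason to leave out those that are incidental.

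**Step 3. Follow one event through the rules.** Take a patient with no previous VTE and no symptoms, in whom an ultrasound shows a new noncompressible segment.

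- Symptomatic DVT rule: not met, because there are no symptoms.
- Incidental DVT, sentence read literally: not met, because the event is not recurrent.
- Incidental DVT, heading joined directly to the finding: met.
- Opening line of the section: no clear help, because the event is not symptomatic and may never have been suspected.

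The same event counts as 0 or 1 depending on whether the site follows the sentence or the heading. The qualifier *(new)* does not settle this. It describes the imaging finding and does not cancel *recurrent*.

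**Step 4. Direction.** The literal reading can only remove events, so the possible error is an undercount of incidental DVT, or a mixture of readings across sites. Symptomatic DVT and all PE categories are unaffected by the word.

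**Step 5. Size.** An estimate would need the incidental DVT rate, the share of these that are first events, and the share of sites using the literal reading. The documents give none of the three, so no figure is computed.

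**The case against.** The strongest reply is that the heading is itself a definition. It announces a finding, and one finding is listed. The parallel incidental PE entry has no confirmation sentence and runs straight from heading to findings. Read the same way, the incidental DVT entry covers every incidental DVT, and *recurrent* is a stray word in a linking sentence. This reading is reasonable and probably the intended one. It means that a reader should not infer that first incidental DVTs are certain to be lost. It does not remove the problem, because the sentence still says something narrower than its heading and nothing tells a site which to follow.

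It can also be said that no ultrasound screening is described, so incidental DVTs would arise only from routine care, and that the case report form, listed in the Appendix but not shown, may handle the matter correctly. Both are fair. They limit how much can be claimed about the effect, but they do not reconcile the two lines.

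Two stronger readings are tempting.

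- *Size.* The background cites a meta-analysis of extended prophylaxis reporting a "significant risk reduction of all VTE (2.6 vs. 5.6" percent, with proximal DVT at 1.4 versus 2.8 percent. From this, 1.4/2.6 = 54% and 2.8/5.6 = 50%, and a reader might conclude that about half of all events are at risk. The ratios do not support that. They do not separate first from recurrent events or incidental from symptomatic ones, and only incidental DVT is touched by the word.
- *Venography.* A reader might infer that omitting it from the DVT rules is a second error. In the PE rules DVT is supporting evidence beside an inconclusive lung scan, whereas in the DVT rules it is the outcome. Different evidence standards for those two roles are not contradictory, and nothing in the documents shows that DVTs seen only on venography will occur at these sites.

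**Conclusion.** The heading and the confirmation sentence for incidental DVT contradict each other, and the sentence is an operative outcome rule. The word *recurrent* is probably a drafting slip, since it appears in no other category and the eligibility criteria give no basis for it. The contradiction permits undercounting or inconsistent classification of first incidental DVTs within one of the study's stated foci. It does not demonstrate that events will be lost, and the size of any effect cannot be estimated from the documents. The conclusion rests on the text of the definitions alone and assumes that the case report form does not already resolve the matter.

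The difference between the DVT and PE rules on venography is a point to clarify, not an error.

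**What to change.** Delete *recurrent* from the confirmation sentence so that it covers incidental DVT in general and matches its heading. The rest of the sentence and the ultrasonography finding can stay as they are. If a restriction to recurrent events was in fact intended, the heading should say so and the plan should state how a first incidental DVT is recorded.

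The cost is one word, with no added imaging or visits. The case report form should be checked for the same wording. The downside is that the reported incidental DVT count may be higher than under the literal reading.

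Separately, the sponsor should reconcile the DVT and PE rules on venography, or add a line stating that ultrasonography alone is intended for DVT as an outcome.

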Ethics committee approval will be obtained where approval of a prospective non-interventional study is required. This study will be conducted in full accordance all applicable Research Policies and Procedures and all applicable laws and regulations. The investigators will perform the study in accordance with this protocol, will obtain consent, and will report unanticipated problems involving risks to subjects or others in accordance with Policies and Procedures and all regulatory

requirements. Collection, recording, and reporting of data will be accurate and will ensure the privacy, health, and welfare of research subjects during and after the study.

Subject Population **Inclusion Criteria**

key criteria for Inclusion and Exclusion:

1. Patients who were diagnosed with histological confirmed high thrombotic risk cancers (GI, thoracic, gynecologic and genitourinary) undergoing surgery
2. Age \geq 18 years

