Major bleeding will be defined as overt bleeding associated with: a fall in hemoglobin of 2 g/dL or more, or leading to a transfusion, or bleeding that occurs in a critical site or contributing to death.

- **Bleeding in a critical area or organ such as:**

Retroperitoneal

Intracranial

Intraocular

Intraspinal

Intra-articular

Pericardial

Intramuscular with compartment syndrome

- **A clinically overt bleeding event**
 - that is associated with a fall in hemoglobin of 2.0 g/dL (>1.24 mMol/L) or more, or
 - leading to a transfusion of ≥ 2 units of packed red blood cells or whole blood.
- **Bleeding contributing to death**

Other clinically relevant non-major bleeding will be defined as overt bleeding not meeting the criteria for major bleeding but associated with medical intervention, unscheduled contact (visit or telephone call) with a physician, (temporary) cessation of study treatment, or associated with discomfort for the patient such as pain, or impairment of activities of daily life. All other bleeding events will be classified as minor

Statistical And Analytic Plan	
Descriptional statistical analysis will be performed for all study data along with epidemiology methods. Continuing parameters will be presented with standards descriptional statistical measures (mean values, median values, percentages etc.) and the results will be presented accordingly into tables. For more complex correlations we will use, among other methods, chi-square tests, ANOVA and t-tests, in order to evaluate the relationships between different patient and disease characteristics, such as:
 
 • Number of patients enrolled • Tumor characteristics • Co-morbidities • Type of Surgical operation • Type of antineoplastic treatment • Type of thromboprophylaxis therapy • Therapy outcomes • Number of therapy disruptions for any reason • Complications (AE- SAE) 
and to present them, accordingly. Due to the fact that this is an observational study the results of all correlations will be carefully discussed and will be used only to assess hypotheses.

REFERENCES	References

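### The bleeding rule can under-grade, and inconsistently grade, serious surgical-site bleeds, because re-operation is not a major criterion and overt is undefined

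*Combined protocol and SAP*

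**What the plan says.** All the grading text is in the Safety Evaluations section of the combined protocol and SAP.

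- **Major, summary sentence.** "Major bleeding will be defined as overt bleeding associated with: a fall in hemoglobin of 2 g/dL or more, or leading to a transfusion", continuing "or bleeding that occurs in a critical site or contributing to death". No number of units is given here.
- **Major, bullets.** The first begins "Bleeding in a critical area or organ such as" and names seven sites: retroperitoneal; inside the skull, eye, spine or a joint; pericardial; and intramuscular with compartment syndrome. The second is "A clinically overt bleeding event", qualified by "that is associated with a fall in hemoglobin of 2.0 g/dL (>1.24 mMol/L) or more, or" a transfusion of at least two units. The third is bleeding that contributed to death.
- **CRNM.** "overt bleeding not meeting the criteria for major bleeding but associated with medical intervention", or with unscheduled physician contact (a telephone call is enough), a pause in study treatment, or discomfort.
- **Residual.** "All other bleeding events will be classified as minor".

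The first inclusion criterion limits the cohort to patients with high-thrombotic-risk cancers ("GI, thoracic, gynecologic and genitourinary) undergoing surgery").

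**The concern.** Bleeding after these operations will often be inside the abdomen, pelvis or chest, and its seriousness may show as a return to theatre. Apart from the retroperitoneal and pericardial entries, the named sites do not cover the operated cavities, and no major criterion mentions re-operation. Re-operation can count only as a medical intervention, which puts it in the same tier as a telephone call. Because overt is required at two levels, a bleed judged not overt misses the Hb and transfusion limbs and CRNM as well, and lands in minor whatever its consequences.

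The stake is the reliability of a stated study focus. Study Objective lists bleedings related to anticoagulation beside thrombotic events. Efficacy Evaluations expressly counts incidental pulmonary embolism and deep vein thrombosis found on imaging. Safety Evaluations does not say whether a bleed found only on imaging is overt. The documents describe no adjudication of bleeds: staff review CRFs for completeness and have no direct access to patient records. Divergent grading between sites would be hard to detect.

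**Working it through.** The documents state no sample size, event count or bleeding rate, so the check is of the rule's logic. The one figure that can be reproduced is the unit conversion: 2.0 g/dL = 20 g/L, and 20 / 16.1145 (haemoglobin monomer, kDa, an assumed constant) = 1.241 mmol/L, which agrees with the printed 1.24.

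**Rule as coded**

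- Major = (overt AND (Hb fall of 2 g/dL or more OR units at or above the threshold)) OR critical site OR contributing to death.
- CRNM = not major AND overt AND at least one CRNM feature, such as an intervention.
- Minor = everything else.

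The threshold is any transfusion under the summary sentence and two units under the bullet, so both were run.

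**All combinations, non-fatal bleed.** Overt (yes/no) × Hb fall of 2 g/dL or more (yes/no) × units (0, 1, 2) × CRNM feature (yes/no) = 2 × 2 × 3 × 2 = 24, of which 12 are overt and 12 concealed.

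| Site treated as | Threshold | Overt (12) | Concealed (12) |
|---|---|---|---|
| Not critical | any transfusion | 10 major, 1 CRNM, 1 minor | 12 minor |
| Not critical | two units | 8 major, 2 CRNM, 2 minor | 12 minor |
| Critical, through the open list | either | 12 major | 12 major |

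The same 12 concealed combinations move from all minor to all major on one judgement about the site. These are counts of criteria combinations, not patient frequencies.

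**Individual records**

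| Record | Any transfusion | Two units |
|---|---|---|
| A. Concealed, unlisted site, Hb fall ≥2 g/dL, 2 units, re-operated | minor | minor |
| B. Overt, unlisted site, Hb fall <2 g/dL, no transfusion, re-operated | CRNM | CRNM |
| C. As B, with 1 unit | major | CRNM |
| D. Overt, Hb fall ≥2 g/dL, re-operated | major | major |
| E. Concealed, retroperitoneal | major | major |
| F. Concealed, fatal | major | major |
| G. Record A, site admitted through the open list | major | major |

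B shows the missing re-operation criterion. A against G shows the dependence on the assessor. C shows the conflict between the two transfusion wordings. D, E and F show what the rule already handles.

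**Effect of defining overt.** If bleeding shown on imaging or at operation counts as overt, concealed combinations found that way follow the overt column: 10 major, 1 CRNM and 1 minor (any transfusion), or 8, 2 and 2 (two units). Record A becomes major on its Hb fall alone. B stays CRNM until re-operation is itself a criterion.

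**The case against.** The strongest reply is that the text forces no wrong grade. The critical-site list is open, and that limb does not repeat overt, so an assessor may grade a serious abdominal or thoracic bleed as major. A bleed seen on CT or at re-operation may also reasonably be called overt. Record B is narrow: it needs an Hb fall under 2 g/dL, no transfusion and a site not admitted as critical. A misgraded bleed is still recorded, and Statistical And Analytic Plan also tabulates complications. The analysis is descriptive, with correlations serving only to assess hypotheses.

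Most of this stands, and it limits the point. A reader might infer that a CT-only pelvic haematoma must be graded minor. The documents do not support that, because the list is open and overt is undefined. What remains is that the same record can receive opposite grades and nothing in the section settles which applies. The open list makes the right grade possible, not reliable.

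It can also be said that making re-operation a criterion is a definitional choice that nothing in the documents requires. That is true. The case for it is that the present text gives re-operation no more weight than a telephone call in a surgical cohort.

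**Conclusion.** The point holds as a cheap improvement. The rule can under-grade serious surgical-site bleeds and can grade identical bleeds differently. The exposure is confined to bleeds that are not fatal, not at a named site, and either re-operated with an Hb fall below 2 g/dL and no qualifying transfusion, or of debatable overtness.

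A reader might go further and infer that major bleeding is under-counted overall, so that prophylaxis looks safer than it is. The documents do not support this. Other wording pushes the count up: any transfusion suffices in the summary sentence, and the 2 g/dL fall has no stated baseline or allowance for operative blood loss. The net direction is therefore unknown.

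The size is unknown too. Suppose 1-3% of patients have concealed or re-operated surgical-site bleeding, 10-50% of it fails every major limb, and 2-3% have other major bleeding. The understatement then runs from 0.1/(0.1 + 3) = 3% to 1.5/(1.5 + 2) = 43%. Every input is an assumption and upward misgrading is ignored, so this range shows only that no figure can be given.

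Nor do the documents call major bleeding the main safety result, or show that comparisons between prophylaxis types are distorted. One rule applies to all patients.

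**What to change.** In Safety Evaluations:

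1. Add a major-bleeding endpoint criterion: surgical-site bleeding that requires re-operation or another invasive procedure to control it. Record it in one CRF field.
2. State that bleeding shown on imaging or at operation counts as overt for the Hb and transfusion limbs and for CRNM. This is better than listing whole body cavities as critical sites, which would make any bleed there major, however small.
3. Keep the residual class as worded. Limiting it to overt bleeds would leave concealed bleeds that are not major with no class.
4. Reconcile the summary sentence, where any transfusion suffices, with the bullet, which asks for at least two units, so that one endpoint threshold applies throughout.

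The cost is a wording change and one CRF field, with no extra patients or procedures. The CRF is not among the documents shown, so whether it already has such a field cannot be checked. The downside is a somewhat higher reported major-bleeding rate. With its own field, the re-operation criterion can be tabulated separately, so the rate without it stays available.
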